4.2 Exclusion Criteria

Clinicians not meeting inclusion criteria above will be excluded from the study.

4.3 Study Enrollment Procedures

Participants will not be enrolled; we will intervene on all clinicians and allied health professionals with prescribing privileges and at least one prescription drug death as part of a public health program to encourage safe prescribing in San Diego County. Informed consent of patients and clinicians is waived under HHS regulations at 45 CFR 46.116(c), as the study is evaluating a County public service safe prescribing program. Deaths where prescription drugs are the primary or contributing cause will be cataloged by the medical examiner between the period of July 1st, 2015 and June 30th, 2016. As part of the County safe prescribing program, prescribers to those deaths are identified in the CURES system. All California pharmacies and clinics that dispense controlled substances must submit reports to CURES on a weekly basis. In consultation with the program manager of CURES, a letter notifying CURES administrators that prescriptions from these clinicians would be evaluated prospectively after the safe prescribing letters were sent was submitted to the CURES system.

5. STUDY INTERVENTIONS

5.1 Interventions, Administration, and Duration

A letter signed by the Chief Deputy Medical Examiner of San Diego County will notify prescribers of the death in their practice. The letter will outline the annual number and types of prescription drug deaths seen by the medical examiner, discussed the value of and way to access the State's prescription drug monitoring program, and discussed five CDC guideline-recommended safe prescribing strategies: 1) Avoid co-prescribing of opioids with benzodiazepines, 2) prescribe minimal dose necessary for acute pain, 3) consider slow tapers with pauses to below 50 MME per day, 4) avoid prescriptions lasting greater than 3-months for

pain, and 5) prescribe naloxone in conjunction with opioids for patients taking ≥ 50 MME per day.

5.2 Handling of Study Interventions

Letters will be carefully edited by an advisory group to ensure tone is supportive and its recommendations consistent with CDC guidelines. Letters will be generated, signed by the San Diego Medical Examiner and posted in the U.S. mail. The pre-intervention baseline period will be 12 months in length with a one year follow-up period to measure the persistence of effects after the intervention.

5.3 Adherence Assessment

Adherence is compulsory as prescription fills are automatically processed through pharmacies in the State and sent to the State’s prescription drug monitoring program.

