6.1.4 Completion/Final Evaluation

A participant is considered to have completed the study if he or she has completed the baseline assessment, received a letter, and been observed for >13 months following letter receipt. The end of the study is defined as completion of the >13-month data observation period following receipt of letter.

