8. INTERVENTION DISCONTINUATION

It is not possible to discontinue intervention because prescribers will receive one instance of the informative communication. In the secondary research design, prescribers will receive a follow up communication if the researchers find another case where an affiliated patient has deceased.

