10.3.5 Monitoring

In addition to data quality reviews, we will also review the integrity of the interventions. It is the primary role of the data analysts to: 1) determine the appropriate number of eligible providers to reach sufficient statistical power, 2) record provider information in a secure, password protected database located at LA County Medical Examiner-Coroner's office and, 3) track enrolled providers in regards to their intervention status and progress. On an approximately quarterly basis, staff would visit headquarters of participating sites and verify functionality of decision support tools. Additionally, practicing clinicians on our study team had the ability to monitor electronic medical record interventions in their own health systems.

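### Section 5.3 takes the capture of prescription fills as adherence, and Section 10.3.5 names no check on mailing or delivery, so the extent of non-delivery of the letter would be unknown when the result is read

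*Combined protocol and SAP*

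**What the plan says.** Section 5.3 is a single sentence, which begins: "Adherence is compulsory as prescription fills are automatically processed through pharmacies in the State". It goes on to say that the fills are passed to the State's monitoring program.

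On delivery, Section 5.2 says: "Letters will be generated, signed by the San Diego Medical Examiner and posted in the U.S. mail". Section 8 adds that "prescribers will receive one instance of the informative communication". It mentions a further letter only for a secondary design, after another death.

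Section 10.3.5 says that the integrity of the interventions will be reviewed. Two concrete checks are named:
- "staff would visit headquarters of participating sites and verify functionality of decision support tools"
- "practicing clinicians on our study team had the ability to monitor electronic medical record interventions in their own health systems"

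The same section also makes the data analysts responsible for a provider database and for following each provider's intervention status.

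Several places rely on receipt. Section 6.1.4 counts a participant as complete who has "completed the baseline assessment, received a letter, and been observed for >13 months following letter receipt". Section 6.1.3 counts follow-up from receipt, and Sections 7.1 and 7.6 compare clinicians who received a letter with controls. Section 9.5 starts the post-period one month after sending, to allow for prescriptions written before the letter arrived.

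**The concern.** Automatic reporting of fills means that the outcome is recorded whether or not a letter was sent, and it does so equally in both arms. It carries no information on exposure to the intervention. Adherence in this trial can only mean that the letter reached the prescriber, and Section 5.3 infers it from an unrelated fact.

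The section that might have made up for this looks in the wrong place. A posted letter has no decision support tool to test at a site headquarters and no medical record component to monitor. The stated procedure is therefore wrong for this trial, not merely short of detail.

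What is at stake is interpretation. If the estimated effect is small, a reader will ask how much of the intervention arm was reached, and the plan specifies no data that would answer.

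**Working it through.** **Where delivery could have been specified**

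| Place | What it covers | Delivery variable named? |
|---|---|---|
| 5.2 | Editing, signing and posting of letters | No |
| 5.3 | Reporting of fills | No |
| 6.1 Schedule of Evaluations | Prescribing, prescriber characteristics, eligibility, randomization, waiver | No |
| 6.1.4 | Makes receipt a condition of completion | No means of establishing it |
| 9.5 | Contrast by intervention group; time runs from sending | No |
| 10.3.5 | Decision support, medical records, providers' intervention status | No; the status item could hold one |

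**Size, for illustration**

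Inputs from Section 9.2: two-sided 5% test, 80% power, 5% difference in means, standard deviation 140 daily MME within cluster, mean cluster size 4.5, coefficient of variation 1.22, intracluster correlation 0.2, and 65 decedents per arm. No allowance for non-delivery is listed.

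The figure of 65 can be neither reproduced nor refuted, because the mean to which the 5% applies is not given. Back-solving shows what it would require:
- Design effect 1 + [(1.22² + 1) × 4.5 − 1] × 0.2 = 3.04. In the Taylor relative-efficiency form, K = 0.9/(0.9 + 0.8) = 0.529, and (1 + 3.5 × 0.2)/(1 − 1.22² × K(1 − K)) = 2.70.
- Effective prescribers per arm: 65 × 4.5/3.04 = 96.2, or 65 × 4.5/2.70 = 108.3 (unrounded design effect 2.702).
- Detectable difference (1.960 + 0.842) × √(2 × variance/effective n): about 53 to 63 MME, with 140 taken as the total or as the within-cluster standard deviation. If the 5% is relative, the implied mean is about 1,066 to 1,264 daily MME.

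The effect of non-delivery does not depend on that mean, so I take 65 per arm at 80% power as given. Let r be the share of letters undelivered. Assume that an undelivered letter has no effect and that non-delivery is spread evenly over clusters. Then:
- effect by assignment = 5% × (1 − r)
- power = Φ[(1.960 + 0.842)(1 − r) − 1.960]
- decedents per arm to restore 80% = 65/(1 − r)², rounded up

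| r (assumed) | Effect by assignment | Power | Decedents per arm for 80% |
|---|---|---|---|
| 0 | 5.00% | 80% | 65 |
| 5% | 4.75% | Φ(0.702) = 76% | 73 |
| 10% | 4.50% | Φ(0.562) = 71% | 81 |
| 20% | 4.00% | Φ(0.282) = 61% | 102 |

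These are worst cases for each r. Section 9.1 accepts that prescribers to the same patient may share information about the letter, so a prescriber whose own letter went astray may still learn of it from a colleague in the same arm.

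**The case against.** The strongest reply is that the effect of mailing is a legitimate target. Sections 4.3 and 6.1.2 present the study as evaluating a County program, and ordinary postal loss is part of what such a program achieves. Section 9.5 compares prescribers by intervention group and excludes nobody for non-receipt. The completion rule in 6.1.4 enters no analysis there. All of this stands.

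It also stands that 10.3.5 is not silent. Tracking each provider's intervention status could be taken to include mailing. But the item names no mailing, return or delivery field and has no use in the analysis, and it sits beside a section that treats adherence as assured. It is the natural place for the missing field, not a substitute for it.

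A reader might infer three stronger things that the documents do not support.
- That a failed mailing could pass for a null result. At an assumed 20% undelivered, a 5% effect becomes 4.0%. That is lost power, not a vanished effect, and every r here is an assumption.
- That many prescribers must have moved or stopped practising by the time of mailing. The documents give no mailing date and no address source, and Section 4.1 sets no interval between prescription and death. The year before death appears only in a planning assumption in 9.2.
- That the effect among those reached can be recovered by dividing by the share of letters not returned. That requires an undelivered letter to have no effect, which sits badly with the sharing allowed in 9.1. A count of letters is also not the matching denominator for a censored model fitted to prescriptions.

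The reference in 10.3.5 to a database in LA County is at odds with 10.1 and 11.3, which keep data at the San Diego office. It should be reconciled, but it is not evidence about delivery.

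**Conclusion.** The point holds as one of measurement and interpretation. Section 5.3 mistakes outcome capture for delivery, and the concrete checks in 10.3.5 do not apply to a mailed letter. As written, the plan specifies nothing that would give the extent of non-delivery.

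It is not a threat to validity: the comparison by assigned arm remains a sound estimate of the effect of mailing. The loss of power, from 80% to between about 76% and 61%, rests on an assumed r of 5% to 20%, on no effect of undelivered letters, on even spread over clusters, and on acceptance of the stated 65 per arm. The true loss may be smaller, and the plan as written could not say. The change should be made because it is cheap and because returned mail that is not recorded as it arrives may be impossible to reconstruct later.

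**What to change.** - **Section 5.3.** Rewrite as delivery adherence. Keep a log by prescriber code with mailing date and return-to-sender status. Re-mail each returned letter once, to the prescriber's current registered address.
- **Section 10.3.5.** Replace the decision support and medical record checks with a review of that log, held at the San Diego office.
- **Section 9.5.** Keep analysis by assigned arm as primary. Count the post-period from the date of the initial mailing for all prescribers, including those re-mailed, so that a re-mail does not shift anyone's window. Report the share of letters returned beside the primary result. Do not add an estimate that divides by that share.

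The cost is modest clerical work. A re-mail replaces a letter that did not arrive, so it fits the single communication described in Section 8. The limitation is that non-return only approximates receipt and cannot show that a letter was read; the report should say so.

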6. STUDY PROCEDURES

6.1 Schedule of Evaluations

Assessment	Baseline	Follow-up:	
		4 Months	12 months
Schedule drug prescriptions	X	X	X
mg MED/MME	X	X	X
Physician specialty	X		
Board certification	X		
Years licensed in state	X		
Prescription drug related death for prescriber	X		
Inclusion/Exclusion Criteria	X		
Enrollment/Randomization	X		
Consent Waiver	X	X	X

6.1.1 Screening Evaluation

All clinicians whom meet the inclusion criteria will be eligible for the trial. Eligibility will be based on historical data from the CURES database.

Consenting Procedure

Not applicable. We will be requesting a waiver of consent under HHS regulations at 45 CFR 46.116(c).

6.1.2 Enrollment, Baseline, and/or Randomization

Enrollment

Participants will not be enrolled; we will intervene on all clinicians and allied health professionals with prescribing privileges and at least one prescription drug death as part of a public health program to encourage safe prescribing in San Diego County. Informed consent of patients and clinicians is waived under HHS regulations at 45 CFR 46.116(c), as the study is evaluating a County public service safe prescribing program.

Baseline Assessments

For the baseline assessment, the study team will evaluate physician prescribing practices in the 12 months pre- intervention using data from the CURES database.

Randomization

For randomization, six decedent lists were generated from the crossed strata levels. Using random.org's sequence generator,(16) true random integer sequences derived from atmospheric noise determined decedent order in each list. For each ordered list, prescribers to decedents in the first half were those who received the intervention.

6.1.3 Follow-up Visits

The follow-up observation period includes evaluating physician prescribing practices in the 13 months following letter receipt.

6.1.4 Completion/Final Evaluation

A participant is considered to have completed the study if he or she has completed the baseline assessment, received a letter, and been observed for >13 months following letter receipt. The end of the study is defined as completion of the >13-month data observation period following receipt of letter.

7. SAFETY ASSESSMENTS

7.1 Specification of Safety Parameters

Although we will be unable to determine if there are hospitalizations or ED visits for opioid withdrawal in patients of clinicians in the intervention group, we will monitor this potential safety issue by comparing clinicians who received a letter to controls to determine if there are any dramatic reductions (>20% from baseline) in opioid prescribing in the post-intervention period as a result of the letter. The U.S. does not have an integrated healthcare system with complete data on hospitalizations for all patients to evaluate induced withdrawal. However, it is possible for us to evaluate if providers induce withdrawal in patients by exhibiting high rates of MME reductions.

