We will conduct a cluster randomized trial of an informative intervention targeting the over-prescription of scheduled drugs with patient death as the unit of randomization.

The follow outcomes will be analyzed:

- 1) Fewer opioid prescriptions written among clinicians receiving the letter, compared to controls;
- 2) Lower cumulative Morphine Equivalent Dose (cMED) among clinicians receiving the letter (as indicated by dosing on prescriptions filled);
- 3) More frequent use of CURES among clinicians receiving a letter;
- 4) Fewer opioid prescriptions for ≥ 100 milligram morphine equivalent (MME)
- 5) Fewer benzodiazepine co-prescriptions

In the main analysis, we will compare a 12-month baseline period to a 12-month post-treatment follow-up period.

Interventions and Duration

The intervention will be a one-time treatment for all participants, with a three-month and a one year follow-up period to measure the persistence of the effects after the intervention.

The following intervention will be analyzed:

A courtesy communication informing prescribers of the death of a former patient where prescription drug overdose was the primary cause or contributed to the cause of the death. The letter will invite prescribers to review materials regarding the clinical guidelines from the Center of Disease Control, the California Department of Public Health, and the San Diego County Prescription Drug Abuse Medical Task Force for a more prudent prescription of those drugs.

Sample Size and Population

Our sample will consist of a heterogeneous group of clinicians and allied health professionals with scheduled drug prescribing privileges practicing in San Diego County who prescribed a Schedule II-IV drug (i.e., drugs as defined by the United States Controlled Substances Act as having an abuse potential, but also a currently accepted medical use) to a person who died as a result of a Schedule II-IV accidental drug death.

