7.6 Safety Monitoring

Although we will be unable to determine if there are hospitalizations or ED visits for opioid withdrawal in patients of clinicians in the intervention group, we will monitor this potential safety issue by comparing clinicians who received a letter to controls to determine if there are any dramatic reductions (>20% from baseline) in opioid prescribing in the post-intervention period as a result of the letter. The U.S. does not have an integrated healthcare system with complete data on hospitalizations for all patients to evaluate induced withdrawal. However, it is possible for us to evaluate if providers induce withdrawal on patients by exhibiting high rates of MME reductions.

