9. STATISTICAL CONSIDERATIONS

9.1 General Design Issues

The study is a decedent-cluster randomized field experiment; clusters of prescribers within each decedent were randomly allocated to either treatment or control. This design avoided treatment contamination—clinicians prescribing to the same patient were able to share information about the intervention without diluting its effect. If two or more decedents had the same prescriber, that prescriber was assigned to one and only one of those decedents by random draw. Two factors served as random strata: 1) whether the decedent received a prescription from a clinician with a single or multiple deaths, and 2) whether opioids only, opioids in combination with benzodiazepines, or benzodiazepines only were the cause of death. The first strata is designed to form equivalent groups on prescriber risk posture. The second strata equated preference for type of scheduled drug prescribed in practice. Strata were crossed to form $2 \times 3 = 6$ randomization groups.

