10. DATA COLLECTION AND QUALITY ASSURANCE

10.1 Data Collection Forms

The Controlled Substance Utilization Review and Evaluation System (CURES) will provide records of opioids dispensed at California pharmacies attributable to each provider in our sample treating all civilian, non-Veteran’s Administration and non-institutionalized patients. CURES is California’s prescription drug monitoring program. The Medical Examiner has authority to use CURES for the purpose of educating practitioners and others in lieu of disciplinary, civil, or criminal actions, in accordance with the California State’s Health and Safety Code § 11165(c)(2). First name, last name, date of birth and address identified each decedent in the medical examiner reports and CURES data. Drug Enforcement Agency (DEA) number identified the prescribers in CURES data. Data from eligible clinicians will be extracted from CURES and kept onsite at the medical examiner’s office for de-identified analytic file preparation. A file stripped of patient and clinician identifiers will be prepared and released for analysis on secure servers at the University of Southern California.

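### The only planned active safety measure counts opioids and cannot register a benzodiazepine reduction, although the letter's first strategy concerns opioid-benzodiazepine co-prescribing

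*Combined protocol and SAP*

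**What the plan says.** Section 7.1 explains that hospital contacts for opioid withdrawal cannot be observed and uses prescribing as a proxy. Clinicians who received a letter are compared with controls to see "if there are any dramatic reductions (>20% from baseline) in opioid prescribing in the post-intervention period as a result of the letter". It adds that "it is possible for us to evaluate if providers induce withdrawal in patients by exhibiting high rates of MME reductions". Section 7.6 repeats this almost word for word. Neither section mentions benzodiazepines.

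The rest of the document is wider than opioids:

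- Section 5.1 lists five strategies that the letter discusses. The first is "Avoid co-prescribing of opioids with benzodiazepines".
- The Précis (Design and Outcomes) lists as its fifth outcome "Fewer benzodiazepine co-prescriptions".
- Section 9.1 stratifies decedents by whether "opioids only, opioids in combination with benzodiazepines, or benzodiazepines only were the cause of death".
- Section 3 states the primary aim in terms of scheduled drugs, not opioids alone.

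On data, Section 10.1 says that CURES "will provide records of opioids dispensed at California pharmacies attributable to each provider in our sample".

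**The concern.** Section 7.1 accepts that a sharp fall in prescribing can bring on withdrawal in patients, and it monitors prescribing for that reason. The reasoning is applied to one drug class only. A prescriber can act on the letter's first strategy by ending the benzodiazepine and leaving the opioid as it was. The safety measure would not change, and under the Précis outcome the same fall would count as a benefit.

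What is at stake is the reach of the safety conclusion. A report that the letter caused no dramatic reductions would be silent on benzodiazepines, and a reader could easily take it to cover them. A finer opioid measure, even one at patient level, would not close this gap.

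**Working it through.** **1. What can move the safety measure.** In either form given in 7.1, the measure is

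opioid change (%) = 100 × (opioid quantity after − opioid quantity at baseline) / opioid quantity at baseline,

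with quantity as prescriptions or MME. The drug list in Section 15 contains opioids only. Benzodiazepine fills enter neither numerator nor denominator, so they cannot affect the result, however large the change.

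**2. Illustration (assumed counts; the documents give none).** Take a prescriber with 20 co-prescribed patients whose opioids stay unchanged.

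| Patients whose benzodiazepine stops | Opioid change | Change in number of benzodiazepine recipients |
|---|---|---|
| 1 of 20 | 0% | −1/20 = −5% |
| 5 of 20 | 0% | −5/20 = −25% |
| 20 of 20 | 0% | −20/20 = −100% |

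The opioid column stays at 0%, against a trigger of more than 20%, in every row. This shows how the measure is defined. It says nothing about how often such changes would occur.

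**3. Other routes by which a benzodiazepine reduction could appear.**

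- Case review (7.3) covers cases found by the stated safety measures. Those are the opioid measures, so a benzodiazepine case does not enter this way.
- Clinician reports (7.3) may concern any event potentially related to the letters, whatever the drug. Section 7.4 sends them to the IRB within a business day. This route is open but passive, depends on the clinician, and gives no rate by arm.
- The co-prescription outcome in the Précis could show a difference between arms if it were analysed. Sections 9.4 and 9.5 specify no analysis of it, a fall would be read as success, and it would miss patients who take a benzodiazepine without an opioid.

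**4. Are benzodiazepine deaths in scope?** Section 9.1 crosses 2 levels of prescriber deaths with 3 causes of death: 2 × 3 = 6 strata, as stated. Benzodiazepine-only strata: 2 × 1 = 2. Strata with any benzodiazepine involvement: 2 × 2 = 4. No number of decedents or prescribers per stratum is given.

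**5. The data descriptions side by side.**

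- 10.1: opioid records for each provider.
- Précis: an outcome that needs benzodiazepine records.
- 6.1: a row for scheduled-drug prescriptions at baseline, 4 months and 12 months, separate from the MME row.
- 10.3.3: quality checks on Schedule II, III and IV drug codes.

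Read literally, 10.1 does not supply what the other three require.

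**The case against.** Several stronger readings are tempting, and the documents do not support them.

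- *There will be no safety information on benzodiazepines at all.* This goes too far. The clinician-report route in 7.3 is open to any drug. What is missing is a planned measure and a comparison between arms.
- *The analytic file cannot hold benzodiazepine data.* A reader of 10.1 alone might infer this. Sections 6.1 and 10.3.3 and the Précis outcome suggest that wider data were intended. The documents establish an inconsistency, not an opioid-only file.
- *A third of the trial concerns benzodiazepine-only deaths.* Two of six strata is a count of randomization lists. It is not a share of decedents, prescribers or patients.
- *The letter tells prescribers to stop benzodiazepines.* Only one of the five strategies mentions them, and it concerns the combination. It could be met by not starting a second drug or by reducing the opioid, which the existing measure could pick up.
- *Prescribers in the benzodiazepine-only strata write few opioids, so an opioid percentage says little about them.* The minimum of one opioid prescription in 4.1 applies to every stratum, and nothing shows lower opioid volumes in these two.

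It can also be said that adding a drug class to a coarse proxy is a matter of preference. That has some force against a formal trigger. It has little against a descriptive table, because the plan already accepts the proxy for opioids and gives no reason to leave out the other drug class named in the letter.

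**Conclusion.** The point holds for planned active monitoring. The one active measure in 7.1 and 7.6 cannot register a benzodiazepine reduction, although the letter's first strategy and the fifth Précis outcome both concern benzodiazepines used with opioids. Such a reduction would surface as a safety matter only through spontaneous clinician reports, so a finding of no dramatic reductions would apply to opioids alone.

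This rests on the definition of the measure and needs no numerical assumption. The frequency or clinical weight of the missed reductions cannot be derived from the documents. The strata counts (2 and 4 of 6) show only that benzodiazepine deaths are in scope. The conflict between 10.1 and the Précis, 6.1 and 10.3.3 stands separately and must be reconciled in any case, because the fifth outcome cannot be computed from opioid records alone.

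**What to change.** In 10.1, state that the CURES extract covers Schedule II-IV fills, including benzodiazepines, for each randomized prescriber, and that the de-identified file carries a coded patient key. Bring 10.1 into line with the Précis outcome, 6.1 and 10.3.3.

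In 7.1 and 7.6, add a descriptive letter-versus-control table in the same windows as the opioid measure, showing:

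- the change in benzodiazepine fills;
- the share of patients with baseline benzodiazepine fills, under a definition fixed in advance, who have no later fill from the study prescriber.

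Where the data allow, show separately the patients who moved to another prescriber, since otherwise a transfer would count as a stop. The 20% opioid figure should not be carried over, because the documents give no basis for it in another drug class. Any threshold for action is for the study team to decide.

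The cost is a larger extract, a coded patient key and one more table. Section 4.3 says that dispensers of controlled substances must report to CURES weekly, and 9.1 treats benzodiazepines as scheduled drugs, so no new data source should be needed.
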